#### C.2.13 Study Timeline (See Table 11).

Table 11. Study Timeline Year 1	1	2	3	4	5	6	7	8	9	10	11	12	Cumulative Number of active Subjects
Study set-up	X	X	X	X	X	X							
*Sleep-Optimize subjects							2	2	2	2	2	2	
*Control subjects							2	2	2	2	2	2	
Total active subjects							4	8	12	16	20	24	
Total subjects YEAR 1							4	8	12	16	20	24	
Year 2	1	2	3	4	5	6	7	8	9	10	11	12	
*Sleep-Optimize subjects	2	2	2	2	2	2	2	1	1	2	2	2	
*Control subjects	2	2	2	2	2	2	2	1	1	2	2	2	
Total active subjects	24	24	24	24	24	24	24	22	22	24	24	24	
Total subjects YEAR 2	28	32	36	40	44	48	52	56	60	64	68	72	
Year 3	1	2	3	4	5	6	7	8	9	10	11	12	
*Sleep-Optimize subjects	2	2	2	2	2	2	2	1	1	2	2	2	
*Control subjects	2	2	2	2	2	2	2	1	1	2	2	2	
Total active subjects	24	24	24	24	24	24	24	22	22	24	24	24	
Total subjects YEAR 3	76	80	84	88	92	96	100	102	104	108	112	116	
Year 4	1	2	3	4	5	6	7	8	9	10	11	12	
*Sleep-Optimize subjects	2	2	2	2	2	2	2						
*Control subjects	2	2	2	2	2	2	2						
Total active subjects	24	24	24	24	24	24	24	20	16	12	8	4	
Total subjects YEAR 4	120	124	128	132	136	140	144						
Year 5	1	2	3	4	5	6	7	8	9	10	11	12	
Data cleaning	X	X	X										
Data analysis			X	X	X	X	X	X					
Manuscript preparation						X	X	X	X	X	X	X	
Final study reports										X	X	X	
Total active subjects													
*Newly enrolled subjects													

**C.2.14 Potential Study Problems and Alternate Approaches.** **1)** Changes in diabetes treatment regimen is a potential influencer in glycemic control during the study period. The participants in the study will receive diabetes treatment per the usual care by their physicians. We will collect the modalities of treatment, changes in treatment, and totally daily insulin doses as covariates when analyzing the primary outcomes. **2)** Design consideration regarding the length of the intervention and A1C measurement: The intervention was designed for a 12-week period to achieve the best possible outcomes based on previous behavioral interventions and feedback from pilot study participants. **3)** The intervention requires smartphones; this could limit the accessibility to non-smartphone users. However, the number of smartphone users has grown significantly in the last decade. It was estimated that 77% of US adults owned a smartphone in 2016, up from 35% in 2011, making the smartphone one of the most quickly adopted consumer technologies. This number is expected to grow; thus, smartphone accessibility will become less of a limitation in the near future. **4)** Obstructive sleep apnea is screened by questionnaire and not the gold standard polysomnography in this study. It is possible that subjects with sleep apnea will be included in the study. However, this will not pose harm to the subjects, and sleep apnea and sleep duration independently contribute to glycemic control. **5.)** In our pilot study we experienced a 10% sensor failure rate. (This is less than that reported by the manufacturer and may be due to the research team's expertise in placing these devices). Most sensor failure was due to dislodgement by the participant. If dislodgement occurs, we will overnight mail a new sensor to the study participant. The dislodged

sensor will retain the recorded data. Participants will be instructed to return the sensor. We anticipate a 24 hour disruption in data collection with dislodgement.

**C.2.15 Future Directions.** Once the intervention is determined beneficial, future directions include deploying sleep optimization to other age groups in T1D, as well as other population with dysglycemia, such as those with type 2 diabetes and gestational diabetes. In the future, using automated prompts with or without human interaction could increase the scalability of this approach. Sleep optimization could be incorporated as a component of standard medical care of T1D.

### 3.1 Protection of Human Subjects

#### 1. Risks to Human Subjects

##### a. Human Subjects Involvement, Characteristics, and Design

**Study Design.** The purpose of this study is to determine the efficacy of a T1D-specific sleep optimization intervention (Sleep-Opt) on the primary outcomes of glycemic control (A1C), sleep variability and sleep duration; and secondary outcomes: other glycemic parameters (glycemic variability, time in range); diabetes distress, self-management behavior, quality of life (QoL) and other patient reported outcomes in working-age adults with T1D and habitual high sleep variability or short sleep duration. The human subjects involved in this research will be working-age adults, 18-65 years with type 1 diabetes (T1D) who report habitual sleep variability (sleep duration SD > 1 hour per week) or sleep duration <6.5h/night during the work days with a desire to improve sleep. To achieve these aims, we will conduct a randomized controlled trial comparing a sleep intervention to a healthy living attention control group.

**Study population.** We plan to enroll up to 300 subjects. We anticipate a 40% screen failure rate and expect to randomize up to 170 for a final sample of 120 subjects with complete data. Inclusion criteria include 18-65 years of age, with a clinical diagnosis of T1D for at least one year, report habitual sleep variability (1 hour/week or more) or sleep duration <6.5h/night during the work days or week days (confirmed with actigraphy), with a desire to sleep longer, and who own a smartphone compatible with Fitbit. Exclusion criteria include insomnia symptoms defined as severe insomnia symptoms as assessed by the Insomnia Severity Index (score  $\geq 15$ ), being at high risk for obstructive sleep apnea as assessed by Stop Questionnaire, a history of severe hypoglycemia (defined as hypoglycemic episodes that result in loss of consciousness within the last 6 months, seizures, or requiring help from others), A1C  $> 10\%$ , rotating shift or night shift work, use of sleep medications/aids, significant renal impairment (estimated glomerular filtration rate  $< 45 \text{ ml/min/1.73 m}^2$ ), significant medical morbidities such as congestive heart failure, cirrhosis, chronic obstructive pulmonary disease requiring oxygen, active treatment for cancer, depression (PHQ8  $\geq 10$ ), history of stroke with neurological deficits, breastfeeding, pregnant or planning pregnancy.

Convenience sampling will be used to recruit subjects throughout the Chicago metropolitan area. We expect that approximately 20% of participants will be recruited from the University of Illinois Medical Center and the remaining from the Chicago metropolitan area. This number is based on our previous study recruitment outcomes. Participants will be randomized to the intervention group or an attention control group to minimize bias. Randomization will be computer-generated in permuted blocks of 4, arranged in random order and stratified by sex. The randomization model will be developed by the study statistician ([name]) and will be executed through the REDCap data management system.

**Site/Setting.** Subjects' home is the study site. All study materials will be mailed to subjects' home and subjects and study staffs will meet via video conference for orientation to the study procedures and instruct subjects how to use the study materials. During the study period, subjects will continue to receive their usual diabetes care with their health care provider. Subjects will be encouraged to discuss any questions regarding blood glucose management with their diabetes health care provider.

##### b. Study Procedures, Materials, and Potential Risks

###### Study Procedures

The sleep optimization intervention employs a wearable sleep tracker (Fitbit), 8 weekly online lessons (over a 12-week period), an interactive smartphone application, and 8 brief telephone counseling sessions tailored to T1D. The intervention will address three specific aspects: sleep variability, sleep duration, and T1D-related

sleep issues such as nocturnal hypoglycemia. Those randomized to the healthy living attention control group will receive 8 weekly online healthy living information lessons (over a 12-week period), and 8 brief phone calls from a health education coach (equal in time and attention to the intervention group). Participants in both groups will be evaluated for sleep parameters, primary outcomes of glycemic control, sleep variability and sleep duration, and secondary outcomes (glycemic variability, time in range, diabetes distress, self-management behavior, QoL and other patient reported outcomes) at baseline (Week 0), Week 6 (mid-treatment), Week 12 (end of treatment), and Week 24 to test the sustainability of the intervention.

## Sources of Materials

Data will be collected from study subjects only for research purposes as follows: (1) self-reported data from questionnaires and the most recent estimated glomerular filtration rate (eGFR), height, and weight from health provider; (2) a fingerstick blood for A1C and urine for pregnancy; (3) continuous glucose monitoring (CGM) from a glucose sensor placed under the skin; (4) wrist actigraphy; (5) Intervention data from the Fitbit and other technologies, as well as coaching calls.

1. Self-reported data will include information collected: (a) during recruitment to establish study eligibility and (b) demographic (age, sex, race, ethnicity), health (diabetes duration, comorbidities, menopausal status, use of sleep aids and caffeine, eGFR, height, weight), key study variables (diabetes distress, self-management behavior, quality of life); and related patient-reported outcomes (anxiety, mood, fatigue, subjective sleep, daytime sleepiness, self-efficacy, hypoglycemic fear, 24 hour dietary recall) collected from questionnaires.
2. Specimens: A1C determined from a fingerstick blood by using standardized procedures. Pregnancy (to confirm eligibility) will be determined from a urine sample using standard procedures. All specimen collection will be conducted by subjects instructed by a trained member of the study personnel using standards for blood borne pathogens.
3. Continuous interstitial glucose levels to calculate glycemic variability and time in range will be obtained from a CGM sensor placed under the skin using standard procedures by trained study personnel. The sensor transmits the glucose levels to a receiver (the size of a quarter) that the subject wears for one week.
4. Sleep parameters obtained through actigraphy (size of a wristwatch worn on non-dominant wrist) will include sleep duration, sleep efficiency, and sleep timing. Standard deviations of these parameters will be calculated and used to reflect sleep variability.
5. Program evaluation obtained from questionnaires and interview.
6. Data collected via the intervention, including frequency and length of use of technologies and coaching data
7. Data to evaluate program outcomes will include (1) recruitment (number recruited, screened, eligible, consented) and (2) retention (attendance and completion rate records) maintained by study personnel.
8. CCTS UIC-Circle data on UI Health patients that may be eligible to participate in our study. This data will be used to mail invitations to participate (See Section C.2.4). The data elements provided by the CCTS will include full name, age, gender, race, ethnicity, address, phone number, and email address if available. Once received from the CCTS the data will be stored securely in REDCap and a Box-Health folder.

## Potential Risks

The potential risks to subjects include:

1. Bleeding, irritation, discomfort, or infection at the fingerstick site and CGM insertion sites. The risk for these problems is very minor and is minimized by following standardized procedures using trained study personnel.
2. Loss of confidentiality. Standard procedures will be used to avoid breaches in confidentiality. We expect this risk to be low.
3. Completing self-report measures on diabetes distress and mood may cause subjects some emotional distress.
4. Risks associated with the intervention may include irritation due to wearing the Fitbit or actigraphy devices.

5. Loss of privacy. Private locations will be used to collect data at all times.

No other risks are currently identified.

## **2. Adequacy of Protection Against Risks**

### **a. Informed Consent**

Subjects (18-65 years) will be recruited from a Chicago metropolitan area university medical center, diabetes clinics, Research Match, local diabetes websites, and organizations, using flyers, e-announcements, and recruitment letters and emails. Potentially eligible interested subjects will be screened by trained study personnel for inclusion and exclusion criteria. Written informed consent will be obtained via online (REDCap) prior to performing any research procedures. The informed consent process will begin when potential subjects are contacted. The researcher will explain the study purpose, procedures, benefits, risks, confidentiality, and research subject's rights. After all questions have been answered and the subject verbally agrees to participate, written consent will be obtained at the via online (REDCap). A copy of the signed consent will be provided to the subject either mail and/or email.

A waiver of informed consent will be requested for the purpose of identifying eligible patients for recruitment from the University of Illinois Health System data base.

### **b. Protections Against Risk**

Methods to minimize risk include:

1. Minimization of bleeding, irritation, discomfort, or infection at the fingerstick site (e.g. A1C) and insertion site (for CGM). The risk for these problems is very minor and is minimized by following standardized procedures. CGM placement and fingerstick will be done using sterile technique and standardized procedures. These will be performed by subjects instructed by trained personnel. Subjects will be instructed to observe their CGM insertion site daily and contact the research personnel if there are signs of bleeding, irritation, redness, or pain.
2. Loss of confidentiality. Strict procedures will be put into place to minimize the risk of breach of confidentiality. All study staff will be trained on methods of maintaining subject confidentiality. Subjects will be assigned a unique code number. A master list that links the subject identity to the data will be kept by the principal investigator (PI) and stored in a locked office separately from the data. **Data storage:** All data will be stored and analyzed by code number. This consists of coded questionnaires, A1C results, actigraphy, and CGM recordings. The coded data will be entered into a password-protected computer with a secure server for analysis. Hard copy (paper copy) data (blood draw results) will be stored in a locked office. Questionnaire data will be collected using Research Electronic Data Capture (REDCap). No identifiers (except subject ID) will be included. Only members of the research team will be able to access these data. **Procedures during data collection:** Privacy will be provided during recruitment by screening potential subjects in a private setting. The screening data that contain personal identifiers will be kept separate from the coded study data and stored in a locked office. All data collection and study procedures will take place in a private location. All data collected via the intervention (e.g., internet intervention materials, data entry, etc.) will be transmitted using Transport Layer Security (TLS) encryption to prevent eavesdropping and tampering with information while it is in the transmission pipeline. To prevent unauthorized access to internet sites, they will be password-protected.
3. Because people with T1D are always at risk for hypoglycemia, study staff will instruct study participants to have fast-acting carbohydrate available should they develop hypoglycemia during a meeting session (either intervention or attention control group).
4. Completing self-report measures on distress and mood may cause subjects some emotional distress. The risk is minimal. In our previous studies with the same population, no subjects reported emotional distress with these measures. However, study staff will be aware of the possibility and address any concerns that are voiced.
5. Should a subject require medical or other professional intervention due to an adverse event or illness, treatment may be obtained through the UIC Medical Center, the subject's regular doctor, or the treatment center or clinic of their choice. Subjects will be provided contact information for the PI should they want to talk to her about their illness or injury.

6. To prevent coercive contact from the application and coach, all email outreach is pre-scripted, and user contact information is never revealed. Outreach emails will state that the coach has noticed they have not worn the Fitbit in a few days and ask if they would like troubleshooting help or to return to the program. It will not include any coercive language or pressure. Email communication will be limited to pre-scripted content reminders and participant outreach.

7. Participants will be informed that they may discontinue the intervention at any time. If an adverse event is experienced, participants will be instructed to contact [name] or [name]. Phone numbers will be provided through which one of the investigators can be reached 7 days/week, 24 hours/day.

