**C.2.7.4 Coaching:** All participants will be assigned to an interventionist who will be a sleep coach to monitor their progress during the study and provide telephone coaching sessions related to their sleep-related goals. Coaches will be recruited, trained, and supervised by [name]. The coaching protocol developed by [name] is based on the principles of Supportive Accountability. The coaches will establish **legitimacy** by their knowledge of sleep and basic counseling principles. They will establish **goals** with the participants based on the participants' values and beliefs, including the sleep-related goals and usage goals (e.g., number of days wearing the sleep tracker). **Performance monitoring** will be completed through an online dashboard visible to the coaches (Fitabase®). The dashboard will contain data from sleep diaries and the wearable sleep tracker. The first coaching session will be a 20-min engagement session, which includes introductions, rationale for the program, clarifying roles of the coach, and the participants' goals for the program. Coaches (directed by [name]) will provide feedback to the participant based on wearable sleep tracker data. For subsequent coaching sessions, the coach and participant will also have weekly brief (5-10 min) follow-up support calls to troubleshoot any problems with the application or wearable sleep tracker, review progress, problem solve barriers to progress, and set goals. Between sessions, the coaches will be available, mostly via email to troubleshoot any problems with the application or wearable sleep tracker. All coaching sessions, text and email communication will be recorded, and a selection of sessions will be coded for intervention fidelity. The use of coaching has been demonstrated to improve adherence to technology-based interventions. [name] has extensive experience in the use of coaching to improve adherence to technology-based interventions.

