**C.2.8 Healthy Living Attention Control.** The research will be conducted remotely by phone call/video conference (Zoom) at participants' preference. The design of the 12-week control group is intended to control for the coach contact in the intervention group, so that we can test the intervention-related components (e.g. motivational enhancement, goal setting, feedback, and sleep education). [name] will train and oversee the coaches for the attention control group. Participants assigned to the health education control group will be provided eight scheduled emails with health education content (e.g. cooking, handwashing, stretching exercises; 8-10 minutes in length) with content written at the 4th grade level or below. Participants will receive eight brief (5- 10 min) telephone contact from the coach (see schedule Table 5) to determine if they received the information and if they had any questions about the materials. The schedule will mirror that of the intervention group. Coaches will not provide counseling or goal setting but may clarify terms or concepts. Participants in the healthy living control group will be instructed not to change their sleep behavior. They will be eligible to receive the sleep intervention at the end of the study. After the final follow-up session, they will receive a Fitbit wearable fitness tracker.

**C.2.9 Measures.** Self-report questionnaires will be used to obtain demographic, literacy, health information, menopausal status, food intake, psychological, behavioral and self-management characteristics (Table 6).

**C.2.9a Primary outcome and additional glycemic measures: Glycemic assessment.** 1.) Glycemic control will be assessed using hemoglobin A1C (A1C; Home Access Health Corp/Everlywell). A1C is a gold standard marker of glycemic control in T1D reflecting average glucose levels in the previous 90 days. 2) **Glycemic variability using CGM (blinded)** will be conducted using FreeStyle Libre Pro glucose sensor or Dexcom (FDA-approved). The sensor tracks glucose concentrations in the interstitial fluid over 24 h using a thin flexible filament (< 0.4 mm thick) inserted into the upper arm (5 mm depth). The system captures glucose levels every 1 minute and records the data every 15 minutes. Variables we will derive from the CGM are mean glucose level, standard deviation (SD), coefficient of variation (CV), percentage of time spent in range (70-180

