### **Monitoring Plan**

The PI, [name], will be the primary monitor and a Data Safety Monitoring Committee will share the responsibility of monitoring the data.

- A Data Safety Monitoring Committee (DSMC) will be appointed to provide oversight and monitoring of the data on an annual basis. The DSMC will consist of: (1) [name], RN, Associate [name] and past Director of Sleep Center, Department of Biobehavioral Health Science, College of Nursing; (2) [name], Associate Professor, Biobehavioral Health Science, College of Nursing; (3) [name], PhD, Dean, College of Nursing, (4) [name], Professor, Division of Endocrinology, Department of Medicine at UIC, and (5) [name], PhD, statistician, Department of Population Health Nursing Science, College of Nursing. Drs. [name] and [name] will meet with the DSMC annually and will present both a written and verbal report. The report will include a summary of cumulative recruitment, randomization, cumulative retention and attrition rate, study group demographics, adverse events, and data completeness and quality. A written report of the meeting will be compiled that summarizes the review of data and outcomes, as well as any recommendations with respect to modification of the protocol.
- Process for Adverse Events. Throughout the study, the PI and Co-Is will monitor the participants for adverse events (AEs). [name] and study staff will review AEs individually in real time and consult with co-investigators as needed. All AEs or unanticipated problems will be reported to the UIC IRB and/or study sponsor as required based on the respective policies and procedures.
- Procedures for monitoring study safety. The facility has protocols in place for responding to emergency events and serious adverse events. These protocols will be followed for the study. All study personnel involved in conducting the research, including recruitment and screening for eligibility, data management, and provision of interventions, will receive training that will address: (1) overview of the

study objectives and procedures, (2) background and training on collecting data free from bias, (3) protection of human subjects and confidentiality, bloodborne pathogen training and infection control procedures (4) instructing study participants in performing fingersticks and placing CGM sensors using infection control procedures, and (5) data and intervention monitoring.

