### **Treatment Fidelity Monitoring**

All coaching sessions (Sleep-Opt and Healthy Living attention control) will be recorded for training and fidelity monitoring. All coaches will be trained until they reach a criterion of adherence to the treatment protocol before being assigned study participants. Biannually, [name] will review approximately 10% of conducted sessions quarterly and code them for adherence using previously developed rating scales. Items include aspects of the session content (e.g., eliciting questions or problems about the intervention, setting goals), structure of the session (e.g., sets an agenda), and therapeutic process (e.g., uses open-ended questions, appropriate session pacing). Control sessions will be reviewed for the presence of sleep-related content or health advice. If any sleep or health advice (other than direction to the source website) is provided, this will trigger re-training. Drs. [name] and [name] will provide bi-weekly supervision to the coaches for their respective groups, providing back data regarding treatment fidelity as well as troubleshooting any clinical issues. A manual of operations will be developed, and staff will be trained on study procedures. All interactions with participants will be scripted when possible. Protocol violations will be reviewed by the staff and reported to the IRB. All interactions by staff with participants will be logged, and emails will be archived.

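### The protocol specifies no scheduled, arm-neutral adverse-event question, so events are likely to be under-recorded and any by-arm tabulation would be open to differential ascertainment

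*Combined protocol and SAP*

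**What the plan says.** **How an event reaches the study team.** Section 3.1, Protections Against Risk, item 7: "If an adverse event is experienced, participants will be instructed to contact" a named investigator, and "Phone numbers will be provided through which one of the investigators can be reached 7 days/week, 24 hours/day". Item 1 of the same list asks participants to watch their CGM site and report problems. Item 5 gives them the principal investigator's contact details in case they wish to talk about an illness or injury.

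**What staff do.** Section 3.3, Monitoring Plan: "Throughout the study, the PI and Co-Is will monitor the participants for adverse events (AEs". It adds that "study staff will review AEs individually in real time". The annual report to the Data Safety Monitoring Committee (DSMC) is to cover, among other things, "study group demographics, adverse events, and data completeness and quality".

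**What coaches do.** In Sleep-Opt (C.2.7.4), follow-up calls are there to "review progress, problem solve barriers to progress, and set goals", among other tasks, and the Week 3 lesson in Table 5 covers nocturnal hypoglycemia and night-time arousals. In control (C.2.8), the calls are "to determine if they received the information and if they had any questions about the materials". Control recordings are checked for sleep or health content (C.2.12 and 3.3): "If any sleep or health advice (other than direction to the source website) is provided, this will trigger re-training".

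**The concern.** Real-time review can begin only once an event is known. If nobody asks, what becomes known depends on which participants choose to call. Such reporting usually misses events, and the loss cannot be repaired at the analysis stage.

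This matters here because the trial aims to lower A1C and change night-time behavior in people with type 1 diabetes. The protocol's account of its own pilot (C.1.4) says that Sleep-Opt participants, with near-optimal baseline A1C, could not safely have gone lower. Hypoglycemia serious enough to need emergency care is therefore something the DSMC would reasonably want counted.

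There is a second issue. A participant in a conversation about progress, barriers and night-time glucose has more occasion to mention an event than one who is asked whether an email on handwashing arrived. A simple count by arm could then differ because of what was heard, not what happened.

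**Working it through.** No adverse-event rate, safety hypothesis or safety sample size is stated, so there is no planned safety figure to reproduce. The check sets the passages side by side and does some counting.

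**1. Is there any scheduled question?**
- Table 3 (C.2.1) lists actigraphy, A1C, CGM and questionnaires.
- Table 6 (C.2.9) lists each instrument and its weeks. None records adverse events. The hypoglycemia scale in it is described as measuring fear of hypoglycemia, not occurrences.
- Sources of Materials (3.1) lists eight kinds of data. Item 7, on program outcomes, covers recruitment and retention. No item covers adverse events.
- CGM yields time below 70 mg/dL in both arms (C.2.9a), but only for one week at each assessment, and it cannot show an emergency visit, an admission or a device-site problem.

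Severe hypoglycemia is screened for at entry, but no listed instrument asks about it after randomization.

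**2. How long is the stretch without scheduled contact?**
The last coaching contact is the Week 12 wrap-up (Table 5), and the next assessment is Week 24. Weeks 13 to 23 number 23 − 13 + 1 = 11, and 11 / 24 = 45.8% of follow-up. The gap is the same in both arms. Talking through the Actiwatch data when the Week 12 device comes back (C.2.9b) may run into the start of it.

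**3. Is the amount of coach contact equal?**
- Table 5 schedules contact in Weeks 1, 2, 3, 4, 6, 8, 10 and 12. That is 8, matching the 8 per arm given under Study Procedures in 3.1.
- Minutes from Table 5: 20 + 6 × (5 to 10) + 10 = 60 to 90.
- Control minutes from C.2.8, where all eight calls take 5 to 10 minutes: 8 × (5 to 10) = 40 to 80.
- Sleep-Opt minutes if the weekly follow-up calls in C.2.7.4 are taken literally: 20 + 10 × (5 to 10) + 10 = 80 to 130, over 12 contacts.

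Contact is equal under Table 5 and Study Procedures, but not under a literal reading of C.2.7.4 and C.2.8. Those passages need to be reconciled.

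**4. Is the content of contact equal?**
No. Sleep-Opt calls review progress and barriers, while control calls are confined to the materials. Outreach for an unworn Fitbit (3.1, Protections Against Risk, item 6) can apply only to Sleep-Opt, because controls receive theirs after final follow-up (C.2.8).

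**5. What would unequal capture do to a by-arm table?**
Let the true risk be p in both arms, and let events be captured with probability s in Sleep-Opt and c in control. The expected recorded risks are p × s and p × c, so the expected recorded risk ratio is s / c. It equals 1 only if s = c. The documents give neither s nor c. The content difference in step 4 makes s > c plausible, but the size is unknown.

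**The case against.** The strongest reply is that the protocol's safety text is brief, not faulty. Monitoring throughout the study is stated, a manual of operations is promised that could hold an event form, risk is described as minimal, and the investigators' phone line is open to both arms around the clock. Much of this stands, and it rules out several stronger readings.

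- **That events are captured solely through participant calls.** A reader might infer this, but the Monitoring Plan says otherwise. What it lacks is a method. Staff also go over Actiwatch data with participants in both arms at each assessment (C.2.9b), which is an incidental, arm-neutral opportunity.
- **That control participants are discouraged from reporting.** The re-training rule concerns advice a coach gives, not events a participant mentions. Nothing tells control coaches to withhold a report. Sessions in both arms are recorded and coaches in both are supervised.
- **That open email access favors Sleep-Opt.** C.2.7.4 offers between-session contact for trouble with the application or tracker, and item 6 confines email to scripted reminders and outreach. This is a weak source of asymmetry.
- **That a planned safety comparison is biased.** C.2.10 and the Addendum contain no by-arm adverse-event analysis, and the DSMC report is not said to be split by arm. The exposure is conditional on someone making such a table.
- **That Weeks 13-23 go unobserved.** The phone line has no stated end date. The period relies on unsolicited reporting, equally in both arms, so by itself it loses events without tilting the comparison.
- **That the distortion can be quantified.** Any ratio would only restate the capture probabilities chosen for it. Nor should weeks without CGM be counted as weeks without safety surveillance, because CGM here is an outcome measure.

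The reply does not supply a scheduled question, form, definition or recall period. None appears in the documents.

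**Conclusion.** The point holds in a limited form. The protocol describes no structured adverse-event elicitation that is the same in both arms. Under-recording is likely in both, most of all over the 11 weeks between the last coaching call and the final assessment. If events are tabulated by arm, for the DSMC or in publication, the difference in call content leaves the table open to differential ascertainment. The likelier direction is more events recorded in Sleep-Opt; the size is unknown.

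This rests on two assumptions: that no event form exists in operational documents outside those reviewed, and that participants who are not asked leave some events unreported. The primary efficacy analyses are not affected. The change is worth making because it is cheap and unsolicited events cannot be recovered later.

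**What to change.** 1. Add one short adverse-event item set, identically worded for both arms, to the REDCap questionnaires already completed at Weeks 6, 12 and 24, and list it in Table 6. Ask about events since the last assessment: severe hypoglycemia, emergency visits, hospitalization and device-site problems. The Week 24 look-back then covers Weeks 13-23.
2. Before writing the hypoglycemia item, reconcile the two definitions of severe hypoglycemia in the exclusion criteria. C.2.3 ends with emergency room visits or hospitalization; 3.1 (Study population) ends with needing help from others.
3. State in 3.3 that any by-arm tabulation uses these solicited reports, with volunteered events listed separately.
4. State in C.2.8, C.2.12 and 3.3 that coaches in both arms pass any reported event to the investigators, and that doing so does not count as health advice under the re-training rule.
5. Reconcile the weekly calls in C.2.7.4 with the eight contacts in Table 5 and Study Procedures, since this decides whether contact is equal.

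The cost is a few questionnaire items at three assessments, one line in the coach scripts and slightly more event processing. The main drawback is recall: 6 weeks at Weeks 6 and 12, and 12 weeks at Week 24.
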